## Supporting Literature

1 \* Provide a summary of current literature related to the research: **If you uploaded a separate research protocol document in the 'Research Protocol' page, cite the applicable section and page numbers from that document in the answer box below.**

One of the co-investigators, [name], recently published an article using a murine model to assess its immune response to a biofilm formation on a prosthetic implant similar to what would be used as orthopaedic hardware. This paper demonstrates a Th1 response during early biofilm formation, with Th2 and Tregs responding later, representing the formation of a chronic biofilm.

2 If available, upload your applicable literature search:

Name	Created	Modified Date
Murine Response to a Chronic Staphylococcus aureus Biofilm Infection.pdf	9/26/2013 6:03 PM	9/26/2013 6:03 PM

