## Lay Summary

1 \* Provide a summary of the background and purpose of the study in language that can be understood by a person without a medical degree.

Surgical site infection in the orthopaedic surgery population is a significant public health issue. Wound infections result in both increased length of hospital stay and total cost of care.

Surgical site infection (SSI) is the most common preventable adverse outcome after a major operation. The economic costs to the US healthcare system are enormous estimated to be in excess of \$1.8 billion per year. For patients who develop an SSI, the cost may be even higher with length of stay and risk of death doubled. Thus the benefits of any intervention decreasing the risk of SSI are very tangible.

A biofilm is a layer of bacteria that adheres to a surface; in Orthopaedics, this often means adherence to implanted metal after fracture surgery. The test that has been designed by one of the investigators on the study has been shown in an animal model to detect the formation of a biofilm up to 1 month prior to clinical detection. Having a blood assay such as this would allow earlier antibiotics and potentially prevent the need for further surgeries to remove metal implants and clean out the biofilm.

ID: VIEW4E02805CF7000  
Name: v2\_Lay Summary

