## Justification, Objective, & Research Design

**If you uploaded a separate research protocol document in the 'Research Protocol' page, cite the applicable section and page numbers from that document in the answer boxes below.**

1 \* Describe the purpose, specific aims, or objectives of this research. State the hypothesis to be tested:

To determine if a new assay to detect early biofilm colonization can be validated in acute postoperative wound infections in orthopaedic trauma patients who have sustained high energy open/closed lower extremity fractures. This would potentially help decrease the amount of surgical interventions needed for infections as it could allow for early intervention and antibiotics.

2 \* Discuss the research design including but not limited to such issues as: probability of group assignment, potential for subject to be randomized to placebo group, use of control subjects, etc.:

A prospective trial conducted at Shock Trauma of patients between 18 years of age and older who have sustained a fracture with metal implanted. We will be collecting between 1-3 routine blood draws for the purpose of laboratory analysis to assess biofilm growth. Patients may be infected or non-infected at the time of blood draw; they will be selected at random for purposes of this study. All patients will be followed as standard of care by their treating physician for all their follow up visits.

3 \* Describe the relevant prior experience and gaps in current knowledge. Describe any relevant preliminary data:

Surgical site infection in the orthopaedic surgery population is a significant public health issue. Wound infections result in both increased length of hospital stay and total cost of care. Specifically, a biofilm assay would help identify early infection in patients and potentially reduce the need for re-operations for infections as it would allow early antibiotic delivery to the affected areas. Our bacteria of focus would be Methicillin-resistant Staphylococcus aureus (MRSA), as this is one of the most predominant organisms in orthopaedic surgical site infections, but can be included to other pathogens causing surgical site infections.

4 \* Provide the scientific or scholarly background, rationale, and significance of the research and how it will add to existing knowledge:

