## Study Procedures

**If you uploaded a separate research protocol document in the 'Research Protocol' page, cite the applicable section and page numbers from that document in the answer boxes below. (If this study is a collaborative UM/VA study please list each procedure that is being conducted and the locations where it is being conducted.)**

1 \* Describe all procedures being performed for research purposes only (these procedures would not be done if individuals were not in the study) and when they are performed, including procedures being performed to monitor subjects for safety or to minimize risks:

Patients will be identified at random in the orthopaedic trauma clinic and current admitted patients who have been diagnosed with an infection. Once eligibility has been confirmed, the informed consent process will be completed by the Research Coordinator and the attending surgeon. Patients will be approached about potential participation in the study as soon as is feasible following determination of eligibility.

Once consented into the study, baseline data regarding participant characteristics, injury characteristics, fracture classification and medical history/co-morbidities will be collected. Characteristics about hospital course and treatment received will also be collected (i.e. blood culture results, antibiotic usage, etc).

At each follow up visit, participants will undergo a clinical evaluation by the treating surgeon as part of standard of care following any surgical procedure and will be interviewed by the research coordinator. Blood draws will be taken at the initial and each subsequent visit and will be analyzed in the laboratory of one of the investigators in the study. If the patient is currently infected currently, or become infected at any point in the future, additional blood draws may be taken, at a maximum of 10 draws, over the period of two years from the clinical diagnosis of infection. The amount of blood that is drawn will not exceed 50 ml or 3 ml per kg in a 8 week period, and collection may not occur more frequently than 2 times per week.

Finally, we would prospectively correlate the laboratory findings with clinical findings by searching the patients' medical records to find outcomes such as a biofilm formation.

2 \* Describe all procedures already being performed for diagnostic or treatment purposes (if not applicable to the study, enter "N/A"):

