As part of the routine standard of care for any patient readmitted to the hospital for suspected surgical site infection cultures are obtained and sent for laboratory analysis to confirm bacterial colonization. As this is an assay to identify earlier a surgical site infection, this would be done earlier than any current testing.

3 \* Describe the duration of an individual participant's participation in the study:

Following index clinic blood draws, patients will be followed during their regularly scheduled visits with their surgeon to assess wound healing.

4 \* Describe the amount of time it will take to complete the entire study:

The study will last 1-2 years in total.

5 \* Describe any additional participant requirements:

There are no additional requirements.

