## Sample Size and Data Analysis

**If you uploaded a separate research protocol document in the 'Research Protocol' page, cite the applicable section and page numbers from that document in the answer boxes below.**

1 \* Provide the rationale and sample size calculations for the proposed target population:

In order to validate the designed test, we hypothesize needing a large study to determine if it is effective in a human model. Additionally, we will follow out the patients to determine if some become infected (the primary outcome of the study that we are trying to ultimately be able to predict. We anticipate 1000-1200 patients enrolled in this study).

2 \* Provide the plan for data analysis. Include in the description the types of comparisons that are planned (e.g., comparison of means, comparison of proportions, regressions, analysis of variance, etc.), which is the primary comparison/analysis, and how the analyses proposed will relate to the primary purposes of the study:

We will describe the population in terms of general descriptive statistics for age, injury, surgery and outcome. We will use t-testing and other statistical analysis as appropriate.

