## Sample Collection/Analysis

You indicated on the "Type of Research" page that your study involves a sample (specimen) collection and/or analysis.

1 \* What type of samples will be involved in this study? (Check all that apply)

Prospective (will be collected)  
 Existing (previously collected at the time of initial IRB submission)

2 \* Will genetic analysis/testing be done on any of the samples?

Yes  No

3 \* Will this study involve banking of samples (storing for future research use)?

Yes  No

4 \* What is the purpose of the sample collection and/or analysis?

The purpose of the sample collection is to culture and determine bacterial colonization or immune response as a proxy for biofilm formation.

5 \* Is there the possibility that cell lines will be developed with any of the samples?

Yes  No

6 \* Will the samples be released to anyone not listed as an investigator on the protocol?

Yes  No

6.1 If Yes, give name(s) and affiliation(s):

7 \* Will the sample material be sold or given to any third parties?

Yes  No

7.1 If Yes, give name(s) and address(es):

ID: VIEW4E0E1A4B80000  
Name: v2\_Sample Collection/Analysis

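### Blood draws are tied to neither surgery nor infection onset and no time adjustment is planned, so the implied infected versus uninfected comparison may mix biofilm phases and may be confounded by time since surgery

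*Combined protocol and SAP*

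**What the plan says.** All references are to the combined protocol and SAP.

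- **Biology.** Supporting Literature, item 1, says that the cited mouse paper "demonstrates a Th1 response during early biofilm formation, with Th2 and Tregs responding later, representing the formation of a chronic biofilm". No days, weeks or effect sizes are given.
- **Readout.** Sample Collection/Analysis, item 4, says the samples serve to "culture and determine bacterial colonization or immune response as a proxy for biofilm formation". No analyte, unit or cut-off is named.
- **Lead time.** The Lay Summary says the test "has been shown in an animal model to detect the formation of a biofilm up to 1 month prior to clinical detection".
- **Entry.** Eligibility admits patients with earlier fixation, without a limit on time since the operation, and also inpatients with a known infection. The design section adds: "Patients may be infected or non-infected at the time of blood draw; they will be selected at random for purposes of this study".
- **Draw timing.** Study Procedures, item 1: "Blood draws will be taken at the initial and each subsequent visit". The visits are routine ones ("patients will be followed during their regularly scheduled visits with their surgeon to assess wound healing"), with no weeks stated.
- **Infected patients.** Study Procedures allows them up to 10 draws over two years, counted from clinical diagnosis. Prospective Samples, item 2, also describes up to three draws during the admission for infection.
- **Analysis.** Sample Size and Data Analysis, item 2: "We will use t-testing and other statistical analysis as appropriate". It mentions no time variable, matching, stratification, covariate or method for repeated draws.

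**The concern.** The aim is early detection, so timing is central to what is being validated. Two separate problems can follow from leaving it out of the analysis.

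**Phase mixing.** If the readout is an immune response that differs between young and chronic biofilm, pooling all draws from infected patients averages the phases. A real early signal is diluted. If the later signal runs the other way, it can cancel.

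**Confounding by time since surgery.** Infected patients can enter through an extra route (as inpatients) and have their own draw schedule, so their draws may fall at different post-operative times from those of uninfected patients. If the marker also moves with recovery from injury and surgery, the groups would differ even if the assay said nothing about biofilm.

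In the first case a useful assay may look weak. In the second a useless assay may look good.

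**Working it through.** **The plan's own figure.** The stated enrolment is 1000 to 1200. It cannot be reproduced, because no alpha, power, effect size, SD or infection rate is given. The arithmetic below is illustrative only. Apart from the total of 1200, every input is assumed: 60 or 100 infected patients, one independent draw per patient, two-sided alpha 0.05, normal approximation.

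**Standard error of the difference, SD = 1:** SE = √(1/n₁ + 1/(1200 − n₁)).
- 100 infected: √(1/100 + 1/1100) = 0.104
- 60 infected: √(1/60 + 1/1140) = 0.132

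**(a) Spurious difference from unequal timing, no biofilm effect.** Assume the marker falls by 1 SD from the early to the late post-operative period, and that the share of early draws is 10, 20 or 30 percentage points higher in infected patients. The spurious shift is 1 SD × 0.10, 0.20 or 0.30, that is 0.1, 0.2 or 0.3 SD. The rejection probability is 1 − Φ(1.96 − shift/SE) + Φ(−1.96 − shift/SE).

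| Shift | 100 infected | 60 infected |
|---|---|---|
| 0.1 SD | 16% | 12% |
| 0.2 SD | 48% | 33% |
| 0.3 SD | 82% | 62% |

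The nominal rate is 5%.

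**Sensitivity to the meaning of 1 SD.** The table holds the total SD at 1. If 1 SD is instead the spread within a phase, mixing phases adds variance. With half the draws early, the total SD is √(1 + 0.5 × 0.5 × 1²) = 1.12. The ranges then become about 14% to 73% with 100 infected and 10% to 53% with 60.

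**(b) Dilution from mixed phases.** Assume a 0.5 SD signal in the early phase, none in the later phase, and half the infected draws in each. The mean difference is 0.5 × 0.5 = 0.25 SD. With 60 infected (5% of 1200), power falls from 97% to 47%. With 120 infected (10% of 1200), it falls from 99.9% to 74%. If the later signal were −0.5 SD in half the draws, the mean difference would be 0.5 × 0.5 − 0.5 × 0.5 = 0.

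**Which clock matters.** The mouse phases run from biofilm formation. The claimed lead time runs back from clinical detection. Recovery from surgery runs from the operation. These are three different clocks, and the plan ties draws to none of them for patients without a diagnosis. For infected patients only the extra draws are counted, from diagnosis.

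**The case against.** Several objections have force.

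- **Confounding is not shown.** A reader might infer that the comparison is confounded by time since surgery. That would need draws from infected and uninfected patients to differ in post-operative timing, and a marker that drifts after surgery without biofilm. The documents establish neither. The differing entry routes and schedules make the first foreseeable. The second is an assumption. This objection stands, and the point is a risk.
- **Implant date is not biofilm onset.** A reader might infer that aligning draws to the implant date would separate the Th1 from the Th2/Treg phase. It would not: infection may begin long after the operation, so a late post-operative draw can come from a young biofilm. This stands and limits the fix. Time since surgery is still the axis on which to make the groups comparable, because uninfected patients have no onset or diagnosis date.
- **The assay may not be immunological.** The stated purpose includes culture and bacterial colonization, and no section says that Th1, Th2 or Treg markers are measured. This stands. The phase argument applies to an immune readout only.
- **The comparison is implied.** The analysis section names no groups and does not say that draws are pooled. The infected versus uninfected contrast is inferred from the design, procedures and analysis sections together. This stands, though it is the natural contrast for the stated aim.
- **Unseen forms.** Additional Documents lists enrolment, infection-diagnosis and follow-up forms that may record the dates. If so, the fix is cheaper, but the analysis section still makes no use of them.
- **Open wording.** Analysis described as whatever is appropriate could include a time adjustment, but it commits to none.

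**Conclusion.** The point holds as a risk that the plan leaves uncontrolled. The proposal cites a response that changes with biofilm age, allows an immune readout, sets no limit on time since fixation, samples infected patients differently, and names only t-testing without a time term. The implied comparison may therefore mix early and chronic phases, and may be confounded by time since surgery.

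The size is illustrative. With 60 to 100 infected of 1200, a 1 SD early-to-late shift and a 10 to 30 point imbalance in early draws, a useless assay would be significant in roughly 10% to 80% of trials instead of 5%. The lower end uses the wider SD of 1.12 and the upper end an SD of 1. The infected counts, the shift, the imbalance and the independence of draws are all assumptions. With no drift or no imbalance, the rate returns to 5%.

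**What to change.** 1. For each draw, derive days since the most recent implant operation from the medical records already being searched. For patients who become infected, also derive days before or after clinical diagnosis.
2. In Sample Size and Data Analysis, item 2, state that the early-detection comparison uses pre-diagnosis draws from patients who become infected, against draws from still-uninfected patients at a similar time since surgery. Do this by matching, or by a model that adjusts for time since surgery and allows for repeated draws from the same patient.
3. Report post-diagnosis draws separately, by time from diagnosis.
4. Do not use fixed time-since-implant windows to label Th1 and Th2/Treg phases.
5. Report separately any patient with no implant operation on record. This is possible because the eligibility criteria are alternatives, and one of them is simply being an inpatient with a known infection.

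The cost is two derived variables and a few sentences of analysis text, with no added visits or blood. The downside is fewer draws per comparison, since post-diagnosis draws leave the early-detection analysis, and slightly more analysis work.

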## Study Procedures

**If you uploaded a separate research protocol document in the 'Research Protocol' page, cite the applicable section and page numbers from that document in the answer boxes below. (If this study is a collaborative UM/VA study please list each procedure that is being conducted and the locations where it is being conducted.)**

1 \* Describe all procedures being performed for research purposes only (these procedures would not be done if individuals were not in the study) and when they are performed, including procedures being performed to monitor subjects for safety or to minimize risks:

Patients will be identified at random in the orthopaedic trauma clinic and current admitted patients who have been diagnosed with an infection. Once eligibility has been confirmed, the informed consent process will be completed by the Research Coordinator and the attending surgeon. Patients will be approached about potential participation in the study as soon as is feasible following determination of eligibility.

Once consented into the study, baseline data regarding participant characteristics, injury characteristics, fracture classification and medical history/co-morbidities will be collected. Characteristics about hospital course and treatment received will also be collected (i.e. blood culture results, antibiotic usage, etc).

At each follow up visit, participants will undergo a clinical evaluation by the treating surgeon as part of standard of care following any surgical procedure and will be interviewed by the research coordinator. Blood draws will be taken at the initial and each subsequent visit and will be analyzed in the laboratory of one of the investigators in the study. If the patient is currently infected currently, or become infected at any point in the future, additional blood draws may be taken, at a maximum of 10 draws, over the period of two years from the clinical diagnosis of infection. The amount of blood that is drawn will not exceed 50 ml or 3 ml per kg in a 8 week period, and collection may not occur more frequently than 2 times per week.

Finally, we would prospectively correlate the laboratory findings with clinical findings by searching the patients' medical records to find outcomes such as a biofilm formation.

2 \* Describe all procedures already being performed for diagnostic or treatment purposes (if not applicable to the study, enter "N/A"):

As part of the routine standard of care for any patient readmitted to the hospital for suspected surgical site infection cultures are obtained and sent for laboratory analysis to confirm bacterial colonization. As this is an assay to identify earlier a surgical site infection, this would be done earlier than any current testing.

3 \* Describe the duration of an individual participant's participation in the study:

Following index clinic blood draws, patients will be followed during their regularly scheduled visits with their surgeon to assess wound healing.

4 \* Describe the amount of time it will take to complete the entire study:

The study will last 1-2 years in total.

5 \* Describe any additional participant requirements:

There are no additional requirements.

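### The analysis plan neither keeps blood drawn after diagnosis out of the early-detection comparison nor says how repeated draws from one patient are analysed

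*Combined protocol and SAP*

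**What the plan says.** **Aim.** Under Justification, Objective, & Research Design, item 1, the question is whether the assay "can be validated in acute postoperative wound infections in orthopaedic trauma patients". Study Procedures, item 2, adds: "As this is an assay to identify earlier a surgical site infection, this would be done earlier than any current testing". Sample Size and Data Analysis, item 1, names later infection as the primary outcome and anticipates 1,000-1,200 patients.

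**Who is sampled.** Recruitment covers the trauma clinic and "current admitted patients who have been diagnosed with an infection" (Study Procedures, item 1). Inclusion criterion 1 also admits inpatients with a known infection. Item 2 of the design section allows a patient to be infected or not when blood is drawn.

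**How often.** The design section says "We will be collecting between 1-3 routine blood draws for the purpose of laboratory analysis to assess biofilm growth". Study Procedures, item 1, says "Blood draws will be taken at the initial and each subsequent visit", and that in patients who are or become infected "additional blood draws may be taken, at a maximum of 10 draws, over the period of two years from the clinical diagnosis of infection". Prospective Samples, item 2, repeats this and also mentions up to three draws during hospitalization for diagnosed infection. Volume and frequency limits are given as well.

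**Analysis.** Sample Size and Data Analysis, item 2, promises descriptive statistics, then t-tests and other methods as appropriate. Study Procedures, item 1, adds that laboratory findings will be correlated with clinical findings from the medical record. Item 3 refers to an index draw ("Following index clinic blood draws, patients will be followed during their regularly scheduled visits") but gives it no role in the analysis.

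**The concern.** Only blood taken before clinical diagnosis can show that the assay detects infection earlier than current testing. A patient enrolled with a known infection has no study blood from before that diagnosis, and a patient who becomes infected on study may add many draws after it. Two separate problems follow if infected patients are compared with the rest without further rules.

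- **Mixing.** Established infection enters a comparison that may be read as early detection. This happens even with one draw per patient.
- **Clustering.** If every draw is a data point, draws from one patient are treated as independent and the t-test rejects too often. This arises from repeated draws in any patient, whatever share is infected.

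At stake is whether a positive result would mean that the assay gives early warning, or only that it differs in patients already known to be infected.

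**Working it through.** **Reproducing the plan's figure.** This is not possible. The 1,000-1,200 comes with no alpha, power, effect size, infection rate or within-patient correlation. The calculations below are illustrations. They assume 1,200 patients (the upper end of the plan's range), 120 of them infected, and a continuous readout. The 120, the effect sizes, the post-diagnosis shares, the correlations and the draw counts as combined are assumptions.

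**1. Mixing, one draw per patient.** Assume no signal before diagnosis and a shift of d SD after it, with a share f of the infected patients' draws taken after diagnosis.

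- SE = √(1/120 + 1/1,080) = 0.0962 SD
- Apparent difference = f × d
- P(significant) = Φ(fd/SE − 1.96) + Φ(−fd/SE − 1.96)
- For d = 0.5 and f = 0.5: 0.25/0.0962 = 2.60, giving 0.74

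| d | f = 0.25 | f = 0.50 | f = 0.75 |
|---|---|---|---|
| 0.5 SD | 0.26 | 0.74 | 0.97 |
| 0.3 SD | 0.12 | 0.34 | 0.65 |

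Simulation (3,000 runs, d = 0.5) gave 0.24, 0.74 and 0.97. Using pre-diagnosis draws only, it gave 0.04 to 0.05, as it must when no pre-diagnosis signal is assumed.

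**2. Clustering, t-test on all draws, no true difference.** Let m1 and m0 be the draws per infected and non-infected patient, n1 = 120, n0 = 1,080, and r the within-patient correlation.

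- Variance ratio = [(1 + (m1−1)r)/(n1·m1) + (1 + (m0−1)r)/(n0·m0)] / [1/(n1·m1) + 1/(n0·m0)]
- Type I error = 2 × (1 − Φ(1.96/√ratio))
- For m1 = 10, m0 = 1, r = 0.3: (3.7/1,200 + 1/1,080) / (1/1,200 + 1/1,080) = 0.004009/0.001759 = 2.28, and 1.96/√2.28 = 1.30, giving 0.19

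| Draws, infected vs not | Ratio, r = 0.3 / 0.5 / 0.7 | Type I error |
|---|---|---|
| 3 vs 3 | 1.60 / 2.00 / 2.40 | 0.12 / 0.17 / 0.21 |
| 10 vs 1 | 2.28 / 3.13 / 3.98 | 0.19 / 0.27 / 0.33 |
| 10 vs 3 | 3.13 / 4.55 / 5.98 | 0.27 / 0.36 / 0.42 |

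Simulation at r = 0.5 (3,000 runs each) gave 0.16, 0.26 and 0.37. The nominal level is 0.05.

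**3. Cost of restricting early detection to incident cases.** Detectable difference at 80% power = (1.96 + 0.8416) × √(1/n1 + 1/1,080).

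| Cases usable for early detection | Detectable difference |
|---|---|
| 120 | 0.27 SD |
| 60 (half already infected at enrolment) | 0.37 SD |
| 40 (20 of those 60 lack a usable pre-diagnosis draw) | 0.45 SD |

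**The case against.** **The plan does not describe either faulty analysis.** The t-test sentence follows a list of descriptive items and does not say what is tested or on which unit. A reader might infer that the plan will treat draws as independent or pool blood from before and after diagnosis. The documents do not say so. What stands is that they exclude neither, and leave the choice of draw open until the data are in hand.

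**Infected patients belong in the study.** A reader might take their enrolment as the error. It is not: the stated aim includes validating the assay in postoperative wound infection, and blood drawn after diagnosis serves that. The 74% is therefore not a false-positive rate for infected against non-infected patients, who do differ under the assumption made. It misleads only as evidence of early detection.

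**The readout may not be continuous.** Sample Collection/Analysis describes culture or immune response as a proxy, so the result could be binary. The SD-based figures would then not carry over directly; the omission would remain.

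**The heaviest sampling is not for everyone.** It is tempting to quote the inflation with 10 draws in every patient (31-47%), but the additional draws are tied to infected patients. The unequal-draw rows are closer to the described sampling.

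**Not all the draw counts conflict.** Up to three draws in hospital can fit within a maximum of 10 over two years. The volume and frequency limits also bound sampling, though they do not cap the number of draws.

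**Conclusion.** The concern holds as an omission with consequences. The study draws blood before and after diagnosis, often more than once per patient, and the written analysis neither separates the two nor allows for repetition. That conclusion rests on the text alone and needs none of the assumed numbers.

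The illustrations show that the effect could be large: about 74% significant results from mixing in the central case (12% to 97% over the inputs tried), and type I error of 12-42% from clustering over the draw patterns and correlations shown. They do not predict what this study will find.

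Separately, two points of consistency are open. One is 1-3 draws in the design section against a draw at each visit plus additional draws in Study Procedures, where it is unclear whether the maximum of 10 is a total or an addition. The other is the two-year window after diagnosis against "The study will last 1-2 years in total".

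**What to change.** In Sample Size and Data Analysis, item 2:

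- Make the patient the unit of analysis.
- For patients not infected at enrolment, base the early-detection comparison only on draws before clinical diagnosis, with a pre-specified rule for using them. One draw in a fixed window is one option. A landmark or time-to-event model using all pre-diagnosis draws is another, and may suit an immune response that changes over time, as the plan's cited murine work describes.
- Analyse patients already infected at enrolment as a separate concurrent-infection comparison.
- Use a mixed model or GEE clustered on patient for any analysis that uses all draws.

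Also reconcile the draw counts across the design, procedures and sample sections, state whether 10 is a total or an addition, and reconcile the post-diagnosis window with the study's length.

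No added sampling is needed, only analysis wording, one further planned comparison and a consistency edit. The real cost is precision: fewer cases remain for early detection, and some incident cases may have no usable draw before diagnosis, so the number that do should be reported.
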